NCT04587752

Cognitive-Behavioral Therapy for Weight-related Bullying

Document date: 6/25/2021

HRP-503B – BIOMEDICAL RESEARCH PROTOCOL
(2017-1)

Protocol Title: Cognitive-Behavioral Therapy for Teens Who Experienced Weight-related Bullying

Principal Investigator: [name]

Version Date: Version 3 (6/17/2021)

(If applicable) Clinicaltrials.gov Registration #: NCT04587752

SECTION I: RESEARCH PLAN

1. Statement of Purpose: State the scientific aim(s) of the study, or the hypotheses to be tested.

The aim of this study is to perform a **clinical trial** to pilot a new cognitive-behavioral treatment (CBT) for weight-related bullying testing (1) feasibility, (2) acceptability, and (3) initial efficacy. Adolescents who experienced weight-related bullying will receive this new treatment.

Hypothesis 1. CBT for weight-related bullying will be **feasible** (participants from target population recruited; intervention reliably delivered).

Hypothesis 2. CBT will be **acceptable** (retention through post-treatment; patient-reported treatment credibility and satisfaction).

Hypothesis 3. CBT will show **initial efficacy** (improvements in general health, post-traumatic stress, weight/shape concerns).

2. Probable Duration of Project: State the expected duration of the project, including all follow-up and data analysis activities.

Two years

[figure not shown]
3. Background: Describe the background information that led to the plan for this project. Provide references to support the expectation of obtaining useful scientific data.

An estimated 36% of youth are bullied (1). Youth with obesity are more likely to be bullied than healthy-weight peers (2-4). Bullying is when a perpetrator with more power intentionally and repeatedly causes harm to a victim (1, 5). Bullying can be physical, verbal or relational (6) and is highly distressing (7, 8). Bullying is a significant *pediatric* public health problem: victims are more likely than non-bullied peers to have social and academic impairment (7, 9, 10), anxiety and depression (11, 12), eating disorders (13), weight gain (4), and poorer overall health (11, 14-16). Bullying is also associated with self-harm and suicide (11, 17, 18). *Childhood* bullying has long-term associations with *adult* health problems: anxiety, depression, self-harm and suicide, poorer overall health, and poorer social functioning (11, 12, 16, 19).

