11	Prevention planning: Set long-term health goals and plans to maintain progress; Identify trauma-related triggers as opportunity to cope
12	Prepare to end treatment: Presentation of bullying narrative by child for parent; Treatment completion celebration

Assessments. Parents and adolescents will be assessed. At the beginning of treatment, adolescents will undergo a clinical assessment to confirm eligibility and to inform the course of treatment. Batteries are guided by *NH ADOPT* workgroup recommendations (45-49). As well as established measures, acceptability (sessions attended; retention; patient/clinician ratings of content), and adherence (e.g., homework completion, clinician recordings coded for reliability and adherence), will be assessed. We will also gather clinical data on the patient's medical history prior to enrollment in the treatment.

Assessment Training: Independent outcomes assessors will receive training in diagnostic interviews from investigators following well-established protocols used in previous projects. Once interviewers are certified in the measures (MINI and EDE), they will receive ongoing supervision to ensure consistent use and prevent drift.

TABLE 2: Assessment Batteries

	Baseline	Month 1	Month 2	Post
Adolescent assessment battery				
Established interviews:				
Eating Disorder Examination interview	*			*
MINI Psychiatric Interview (MINI)	*			
Medical history	*			
• Columbia Suicide Severity Rating Scale (Columbia)	*	*	*	*
Established survey measures:				
• Children's Impact of Event Scale-13 (CRIES)	*	*	*	*
• Kirby Delay Discounting	*			*
• Questionnaire for Eating and Weight Patterns (QEWP-5)	*			*
• Eating Disorder Examination—Questionnaire (EDE-Q)	*	*	*	*
• Patient Health Questionnaire-9 (PHQ-9)	*	*	*	*
• Rosenberg Self-Esteem Scale (RSES)	*	*	*	*
• EARLY	*	*	*	*
• Perceived Stress Scale (PSS)	*			*
• Amsterdam Executive Function Inventory (AEFI)	*			*
• Sensitivity to Reward/Punishment (SRSPQ)	*			*
• Perceptions of Teasing Scale (POTS)	*	*		*
• Weight-related Victimization	*			*
• Weight Bias Internalization Scale (WBIS)	*	*		*
• Brief Resilience Scale (BRS)	*	*	*	*
• Self-compassion Scale (SCS)	*	*		*
• Self-Efficacy Questionnaire for Children (SEQ-C)	*	*		*
• CHAOS Scale	*			*
• Clinical Impairment Assessment (CIA)	*	*		*
• Palatable Eating Motives (PEMS)	*	*		*
• Medical Outcomes Study Short-Form (SF12)	*			*

Anthropometric: BMI-z	*	*	*	*
Acceptability:				
• Treatment credibility	*			

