The PI is responsible for monitoring the data, assuring protocol compliance, and conducting the safety reviews. During the review process, the PI will evaluate whether the study should continue unchanged, require modification/amendment, or close to enrollment.

The PI will provide a summary of the DSMP report to the Yale IRB on a yearly basis. The DSMP reports will include Subject accrual, Treatment completion rates, Interim analyses, and Adverse and serious adverse events. These reports will be discussed with the mentoring team during regular meetings and sent to the Safety Monitor for review. The frequency of data review is summarized in the following table:

	Data Type	Frequency of Review by PI	Frequency of Review by PI and Safety Monitor
1	Subject accrual	Monthly	Annually
2	Treatment completion rates (retention/attrition)	Quarterly	Annually
3	Interim analyses	Twice Yearly	Annually
4	Adverse and serious adverse event rates	As needed	Annually
5	Checklist for Safety Monitor	NA	Annually

The PI, the Institutional Review Board (IRB) and/or the Safety Monitor have the authority to stop or suspend the study or require modifications.

Subject Accrual

Subject accrual reviews will help to assure that subjects are being enrolled (accrued) at a rate necessary to meet the recruitment goals in general and with regard to racial/ethnic diversity. Subject accrual rates will be discussed with the PI monthly and annual accrual rates will be reported by the PI to the Safety Monitor to determine if any corrective action is needed to meet the recruitment goals.

Treatment Completion Rates

Retention, attrition and completion rates will be carefully tracked and reviewed. This will be done quarterly to highlight any possible concerns and will be reviewed formally with the PI and Safety Monitor annually. Differential dropout across treatments and/or higher than expected dropout will be reviewed to determine whether any problems are present and what, if any, corrective action needs to be taken. "Trigger points" for corrective action, as described below, include: 35% ("low alert"), 40% ("mid alert"), 45% ("high alert"), and

50% ("extreme alert"). With early alerts to problems, action would be taken to avoid higher level alerts; if a higher-level alert should arise, more drastic actions would be taken.

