It is possible that baseline differences between the treatment conditions, excessive attrition, and/or missing data will limit the value of the data analysis, and hence knowledge to be gained from this study. For these reasons, interim analyses will be conducted twice yearly. Baseline differences, if present, will be considered in relation to potential effects on the power to detect differences in the primary outcomes. If these effects were to develop and be sizeable, alterations to the randomization schedule would be considered. Such effects would be evaluated and discussed by the PI and mentors, and plans would be communicated to the Yale IRB. To address excessive attrition and missing data, the following actions would be taken at the "trigger point" for each level of alert:

- 1) Low-level alert (35%): Review of potential problems by PI and review of procedures for supervision of study clinicians.
- 2) Mid-level alert (40%): Meeting between PI and senior study team members to discuss approaches to minimize further dropouts.
- 3) High-level alert (45%): Meeting between PI, safety monitor, and senior study team members to determine further alterations to study protocol to complete the study with no further losses.
- 4) Extreme-level alert (50%): In the unlikely event that a 50% dropout rate occurs prior to the mid-study time point, the PI and senior study team members would convene to discuss the usefulness of continuing the study.

It is possible that other situations could occur that might warrant stopping the trial. Any concerns would be discussed with appropriate parties (PI, Mentors, Safety Monitor, Yale IRB).

Measurement and Reporting of Adverse Events

Data on adverse events will be collected on an ongoing basis. Adverse events data will be monitored by the PI and reviewed with the Safety Monitor throughout the pilot RCT (see Table above).

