Study participant safety will be monitored by the study team and reported to the PI at all clinical and assessment visits and referrals will be provided if warranted and/or requested. If a study participant experiences any psychiatric symptoms or distress (e.g., depressive symptoms or suicidality) at any stage of study participation he/she will receive short-term treatment and support from the study treatment team (which includes psychologists) and will be connected to a local emergency department (e.g., the Crisis Intervention Unit at Yale-New Haven Hospital) and her pediatrician or therapist for ongoing care.

Other Potential Issues Relating to Stopping Rules for the Study Include:

- 1) New Information: It is unlikely that any new information would become available during this trial that would necessitate stopping the trial. If new data become available, these will be evaluated.
- 2) Limits of Assumptions: It is possible that baseline differences between the treatment conditions, excessive attrition, and/or missing data could limit the value of data analysis. Baseline differences across treatment groups, if present, will be evaluated twice yearly and considered in relation to potential effects on the power to detect differences in the primary outcomes. If these effects were to develop and be sizeable, alterations to the randomization schedule would be considered.

Limits of Rules: There are other situations that could occur that might warrant stopping the trial and/or including a section on the safety report entitled “Other situations that have occurred since the last safety report that warrant discussion” to allow for communication of concerns.

13. Statistical Considerations: Describe the statistical analyses that support the study design.

Continuous variables will be examined for normality using probability plots and Kolmogorov-Smirnov tests. If normality is not satisfied and transformations do not achieve acceptable normality, nonparametric strategies will be considered. Analyses will be intent-to-treat. Outcomes will be tested at the $\alpha=0.05$ threshold.

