As this is a pilot study, results are anticipated to yield significant impact by providing effect sizes that will allow outcome variables to be selected and sample size to be calculated for a fully-powered randomized controlled trial that includes a control group. Descriptive statistics will characterize putative outcome variables (Aim 1: general health, trauma symptoms, weight/shape concerns) and variability, including confidence intervals. Exploratory analyses will identify potential outcome, predictor, and moderator variables to be tested in an adequately-powered RCT comparing CBT for weight-related bullying with a control group in preventing disordered eating and weight gain.

Variables and Analyses for Primary Aims. (1) **Establish** feasibility: descriptive statistics will quantify total/last sessions attended, and clinician adherence (ratings of recorded sessions). (2) Acceptability: descriptive statistics will quantify treatment ratings (clinician/patient). (3) **Test** initial efficacy at post relative to baseline on clinical outcomes: descriptive statistics (means and variability, including confidence intervals) will characterize change and paired t-tests will test changes from baseline to post in (a) improvements in general health (SF12), (b) reductions in traumatic symptoms (CRIES) and (c) reductions in weight/shape concerns (EDEQ). Repeated-measures growth mixture models (103) will explore response over time for these three variables (SF12, CRIES, EDEQ). This approach allows for different numbers of observations per participant, uses all available data on each participant, accounts for clustered data observations (e.g., parent-child), and is unaffected by data missing at random. Because we cannot *a priori* predict the shape of the response over time, we will first treat time as categorical and then test for polynomial trends. Attendance will be examined for informative dropout patterns.

Variables and Analyses for Secondary Aims: **Explore** whether clinical features improve with treatment: descriptive statistics (means and variability, including confidence intervals) will characterize change and paired t-tests will test changes from baseline to post in (1) eating disorder behaviors (episode frequency), (2) depression (PHQ), (3) weight (BMI-z). As with primary aims, repeated-measures growth mixture models will explore response over time for these variables.

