Power Analysis and Justification of Sample Size for Pilot Study. Power estimates for the pilot RCT were based on change in weight concerns during CBT-ED for adolescents (104). Assuming a two-sided test at $\alpha=0.05$ threshold, we have 80% power to detect clinically-meaningful within-subject effects ($d=0.64$) with a sample size of 23. With a sample size of 30, we have 80% power to detect clinically-meaningful effects if there is 20% dropout. Thus, we have a reasonable chance of finding statistically significant change, even in this pilot study.

SECTION II: RESEARCH INVOLVING DRUGS, BIOLOGICS, RADIOTRACERS, PLACEBOS AND DEVICES

If this section (or one of its parts, A or B) is not applicable, check off N/A and delete the rest of the section.

A. RADIOTRACERS N/A

B. DRUGS/BIOLOGICS N/A

B. DEVICES N/A

SECTION III: RECRUITMENT/CONSENT AND ASSENT PROCEDURES

1. Targeted Enrollment: Give the number of subjects:

- Targeted for enrollment at Yale for this protocol: **30**
- If this is a multi-site study, give the total number of subjects targeted across all sites: n/a

2. Indicate recruitment methods below. Attach copies of any recruitment materials that will be used.

 Flyers	 Internet/web postings	 Radio
 Posters	 Mass email solicitation	 Telephone
 Letter	 Departmental/Center website	 Television
 Medical record review*	 Departmental/Center research boards	 Newspaper
 Departmental/Center newsletters	 Web-based clinical trial registries	 Clinicaltrials.gov
 YCCI Recruitment database	 Social Media (Twitter/Facebook):	

 Other: EPIC direct-to-patient	
 Other: messages to provider EPIC inbox	

* Requests for medical records should be made through JDAT as described at
<http://medicine.yale.edu/ycci/oncore/availableservices/datarequests/datarequests.aspx>

3. Recruitment Procedures:

- Describe how potential subjects will be identified.

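### Does leaving retention out of the acceptability analysis leave Hypothesis 2 without a usable reading?

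*Combined protocol and SAP*

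**What the plan says.** Section 1 (Statement of Purpose) lists the outcomes for Hypothesis 2, acceptability, as "retention through post-treatment; patient-reported treatment credibility and satisfaction". Section 4 (Research Plan, Assessments) again places retention there, with "acceptability (sessions attended; retention; patient/clinician ratings of content".

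In section 13 (Statistical Considerations), the primary-aims paragraph gives acceptability one line: "2) Acceptability: descriptive statistics will quantify treatment ratings (clinician/patient". Attendance comes under feasibility, where "descriptive statistics will quantify total/last sessions attended, and clinician adherence (ratings of recorded sessions". The same paragraph ends by saying that attendance will be checked for informative dropout. Section 13 also states: "Analyses will be intent-to-treat".

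Dropout figures appear in two other places:

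- The power paragraph of section 13 says "With a sample size of 30, we have 80% power to detect clinically-meaningful effects if there is 20% dropout", after giving 23 as the number needed for d = 0.64.
- Section 12 (Data and Safety Monitoring Plan) says "Retention, attrition and completion rates will be carefully tracked and reviewed" and sets alerts at 35%, 40%, 45% and 50%. The first reads "Low-level alert (35%): Review of potential problems by PI and review of procedures for supervision of study clinicians".

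**The concern.** Acceptability is one of three aims, and retention is the first outcome named for it. The section that says how each aim will be analysed omits it. It does not say whether a loss means stopping sessions or missing the Post assessment, what the denominator is, or what rate would support the hypothesis.

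The two kinds of loss can differ. Families are paid per assessment (Section VI, Payments for Participation), so a teen who stops sessions may still complete Post. If the definition is open, it could be settled after the data are seen. With 7 to 10 losses, the authors could call retention worse than planned (above 20%) or point out that no alert was reached (below 35%). A loosely defined rate would also be a poor guide to the dropout allowance of the later randomised trial.

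**Working it through.** **The plan's sample size.** Inputs from the power paragraph: d = 0.64, two-sided alpha 0.05, 80% power, paired test. The normal approximation gives n = ((1.960 + 0.842)/0.64)² = 19.2, so 20. The noncentral t distribution gives 22 as the smallest n with at least 80% power, and 83.5% power at the stated 23. Inflating for dropout, 23/0.80 = 28.75, so 29; and 30 × 0.80 = 24 completers. The stated 23 and 30 hold, slightly on the safe side.

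**Losses against the two percentages.** Loss rate is k/30. The interval is the exact (Clopper-Pearson) 95% interval for dropout. Power is for d = 0.64 with 30 − k completers.

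| Losses k | Rate | 95% interval | Completers | Power |
|---|---|---|---|---|
| 6 | 20.0% | 7.7–38.6% | 24 | 85.1% |
| 7 | 23.3% | 9.9–42.3% | 23 | 83.5% |
| 8 | 26.7% | 12.3–45.9% | 22 | 81.6% |
| 9 | 30.0% | 14.7–49.4% | 21 | 79.7% |
| 10 | 33.3% | 17.3–52.8% | 20 | 77.5% |
| 11 | 36.7% | 19.9–56.1% | 19 | 75.1% |

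Seven to 10 losses do lie above 20% and below 35%; the first alert is reached at 11. But 7 losses leave exactly the 23 completers the plan asks for, and computed power first drops below 80% at 9. Every interval in the 7-to-10 band contains both 20% and 35%.

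**If each percentage were used as a pass mark.** With losses binomial (30, p), passing means at most 6 losses under one rule and at most 10 under the other. True rates other than 20% are assumptions.

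| True loss p | P(at most 6) | P(at most 10) | Difference, P(7 to 10) |
|---|---|---|---|
| 20% | 60.7% | 97.4% | 36.7% |
| 25% | 34.8% | 89.4% | 54.6% |
| 30% | 16.0% | 73.0% | 57.1% |
| 35% | 5.9% | 50.8% | 44.9% |

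The last column looks serious, but it compares two rules that the plan does not contain. The 20% is a condition in a power statement; the 35% prompts a review of supervision. Neither is offered as a test of acceptability, and being under an alert is nowhere equated with being acceptable.

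**The definition of loss.** Suppose 10 of 30 stop sessions and 0 to 5 of them still give Post (both assumed). Loss by the Post definition is then 10/30 = 33.3% down to 5/30 = 16.7%. The swing depends on those assumed counts, and the text favours one definition. The hypothesis speaks of retention up to post-treatment, Table 2 has a Post assessment, and intent-to-treat points to all enrolled as the denominator. Stopping sessions is described separately, by total and last sessions attended.

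**The case for a change.** The best case for a change is that Hypothesis 2 is a claim, not just a quantity to estimate. Its first-named outcome should then have an analysis line, a definition fixed in advance and a stated reading. A few sentences would supply all three, at no cost in data or visits. Sessions attended is only a proxy, since it shows exposure and not whether Post was obtained. The check of attendance for informative dropout serves the efficacy models and yields no retention rate.

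Part of this stands. The omission is plain on the page, the definition has to be inferred, and a sentence on it would be tidy.

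The rest does not carry. No feasibility or acceptability measure in section 13 has a pass mark; all are described, not tested. A rule of at most 6 losses would be missed in 39.3% of trials (100% − 60.7%) when dropout is exactly the planned 20%. The natural alternative, estimation only, is close to what section 13 already does for the other acceptability measures. As for the later trial, the stated purpose of the pilot is to supply effect sizes for choosing outcomes and calculating sample size. A plain retention count would serve any dropout allowance, and 30 participants would leave it imprecise under any wording.

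**Conclusion.** No change is needed. Section 13 omits a named outcome from its acceptability line, but the outcome is tracked, its natural definition can be read from the hypothesis, Table 2 and the intent-to-treat statement, and analysts would report it as a proportion of those enrolled. The 20% allowance and the 35% to 50% alerts do not contradict each other, and none of them is an acceptability rule.

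The effect is confined to how one descriptive rate is presented. At 24 of 30 retained, exactly as planned, the exact 95% interval for retention is 61.4% to 92.3%, so a benchmark would seldom settle the matter. No efficacy test, sample size or alert level is affected.

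This conclusion assumes that retention is reported as Post assessments obtained over all enrolled, with sessions attended shown alongside. A report that used only the more favourable of the two would deserve criticism, but nothing in the plan directs that.

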TF-CBT is an established treatment for trauma-related concerns, and CBT-ED are established treatment for disordered eating. TF-CBT is widely used in youth, and CBT-ED is widely used in research and clinical settings, for both youth and adults. The only foreseeable risks include some discomfort or embarrassment when discussing bullying, eating patterns, weight, or body image concerns.

Previous controlled clinical trials conducted by the PI and study team with similar interventions with adult and adolescent participants have not reported problems. Any troublesome effects would be readily identifiable by the experienced study clinicians during repeated evaluations. Thus, the risks of the CBT intervention are judged to be minimal.

Research assessments are noninvasive and should add no substantial risk. The major disadvantages are the time taken to complete them and potential for a breach of confidentiality. Completion of the assessment interviews and surveys may cause some mild anxiety or embarrassment to some participants. Past experiences of the PI and study team indicate that the measures are acceptable to participants. Careful efforts aimed at maintaining confidentiality will be made (as described below).

There is a chance that participants' mood or eating concerns may fail to improve or may worsen during the study. Participants will be provided with short-term treatment and support from the PI and clinical team (which includes psychologists) and/or the participant will be withdrawn from the study if their clinical condition deteriorates to a significant degree. Any participant who is withdrawn will be provided with appropriate referrals.

11. Minimizing Risks: Describe the manner in which the above-mentioned risks will be minimized.

The study clinicians will be carefully trained and supervised by the PI. All study clinicians and study staff will have IRB and ethics training; because of their educational experience and training (e.g., in psychology), they can reasonably be expected to identify potential problems and to take appropriate action as medically indicated.

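### The efficacy paired t-tests use only teens with both Baseline and Post scores, while the planned all-available-data models for the same outcomes have only an exploratory role

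*Combined protocol and SAP*

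**What the plan says.** All references are to the combined protocol and SAP.

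- **Test.** Section I, item 13, assigns the test of initial efficacy to complete pairs: "paired t-tests will test changes from baseline to post in (a) improvements in general health (SF12", followed by CRIES and EDE-Q. The secondary outcomes follow the same pattern.
- **Principle.** The same item states "Analyses will be intent-to-treat" and does not define the term.
- **Models.** "Repeated-measures growth mixture models (103) will explore response over time for these three variables (SF12, CRIES, EDEQ". The approach "uses all available data on each participant, accounts for clustered data observations (e.g., parent-child), and is unaffected by data missing at random", and "we will first treat time as categorical and then test for polynomial trends".
- **Dropout check.** "Attendance will be examined for informative dropout patterns". No analysis step is tied to the result.
- **Use of the results.** The pilot is to have impact by "providing effect sizes that will allow outcome variables to be selected and sample size to be calculated" for a later controlled trial.
- **Ways to lose a Post score.** Item 11 lets teens leave whenever they wish. Item 10 offers short-term support "and/or the participant will be withdrawn from the study if their clinical condition deteriorates to a significant degree". It does not say whether Post is then still assessed.
- **Schedule (Table 2).** CRIES and EDE-Q are taken at Baseline, Month 1, Month 2 and Post. SF12 is taken at Baseline and Post only.
- **Sizing.** 23 teens for 80% power at d = 0.64 (two-sided 0.05), and 30 enrolled to allow for 20% dropout.

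**The concern.** A paired t-test drops every teen without a Post score. That sits awkwardly with an intent-to-treat statement, and nothing in the plan closes the gap. The analysis that does keep such teens is described as exploratory, so it is not the one that yields the efficacy test.

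In a single-arm study there is no comparison group in which selective loss might cancel out. If teens who were doing poorly are the ones without Post, mean improvement is overstated. If teens leave because they feel better, it is understated. The effect sizes are meant to help choose outcomes and size the next trial, so the estimate matters as much as the p-value. For CRIES and EDE-Q the paired test also sets aside Month 1 and Month 2 scores that carry information about a missing Post.

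**Working it through.** **1. The plan's own figure.** Paired t-test power from the noncentral t distribution with n − 1 df and noncentrality d√n, at d = 0.64 and two-sided 0.05: n = 22 gives 81.7%, n = 23 gives 83.5%, n = 24 gives 85.1%. The stated 23 is slightly conservative. Dropout: 23/(1 − 0.20) = 28.75, so 29, against 30 enrolled; and 30 × 0.80 = 24 remain. The sizing reproduces, and it fits a test on completers.

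**2. Bias of the paired test: assumptions.** The documents give no rate of outcome-related leaving and no within-person correlation, so these are assumed.
- 30 teens, four visits, normal scores, true change zero.
- Six have no Post score (the plan's 20%).
- m of the six (0, 1 or 2) are the teens with the poorest interim change; the rest are random.

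Let r be the correlation between the interim change that drives leaving and the Baseline-to-Post change. The expected values of the two lowest of 30 standard normals are −2.043 and −1.616. All 30 changes average zero, so removing the m poorest leaves

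bias = r × (2.043)/29 for m = 1, and r × (2.043 + 1.616)/28 for m = 2, in SD of change.

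Random losses do not alter this expectation, so ten missing (33%, still under the first 35% alert in item 12) gives about the same bias.

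**3. Values of r.**
- Constant between-visit correlation ρ: each change has variance 2(1 − ρ) and any two have covariance 1 − ρ, so r = 0.50 whenever the teen leaves.
- Correlation decaying as AR(1), leaving on Month 2 change: r = (1 + ρ − ρ² − ρ³) / (2√[(1 − ρ²)(1 − ρ³)]).
- AR(1), leaving on Month 1 change: r = (1 − ρ + ρ² − ρ³) / (2√[(1 − ρ)(1 − ρ³)]).

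**4. Results.** Bias is from the formula. False improvement is the simulated rate of rejecting in the favourable direction (40,000 runs per case, nominal 2.5%).

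| Assumed case | r | Bias, m = 1 / 2 | False improvement, m = 1 / 2 |
|---|---|---|---|
| Constant 0.5 or 0.7 | 0.500 | 0.035 / 0.065 | 3.8–3.9% / 5.1–5.3% |
| AR(1) 0.7, leaves on Month 1 | 0.503 | 0.035 / 0.066 | 3.9% / 5.4% |
| AR(1) 0.85, leaves on Month 1 | 0.537 | 0.038 / 0.070 | 3.9% / 5.5% |
| AR(1) 0.7, leaves on Month 2 | 0.749 | 0.053 / 0.098 | 4.7% / 7.7% |
| AR(1) 0.85, leaves on Month 2 | 0.784 | 0.055 / 0.102 | 4.6% / 8.1% |

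With m = 0 the bias is zero and the rate about 2.5%. If the same number leave because they improved, the bias changes sign.

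**5. Scale.** The sampling SD of the observed d with 24 teens at d = 0.64 is 0.237 (SD of the noncentral t on 23 df, divided by √24).

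**6. What a four-visit model does.** Simulated with an unstructured covariance, using a closed-form likelihood estimate in place of REML:
- Bias stays within 0.01 SD, also when leavers go early. When only Post is missing, false improvement is 2.1–2.7%.
- The standard error is about 0–6% smaller than for the paired test.
- If leaving is tied to the unseen Post change (assumed correlation 0.5), bias falls only from 0.03–0.07 to 0.02–0.04 SD.
- A random intercept alone is not safe: under AR(1), false improvement is 5.6–6.5% even with random dropout.

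**The case against.** The strongest reply is that most of this is already planned. Models for the same three outcomes, using all available data and starting with categorical time, are listed under the primary aims, together with a dropout check. That first step could already give a Post-versus-Baseline contrast on every teen. This stands in large part: what is missing is which analysis is the main one. It does not settle the matter, because the plan gives the models an exploratory role, and the reference for growth mixture models concerns latent trajectory classes. The plan never says that one contrast will be reported as the efficacy estimate.

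It is also fair that the sizing openly counts dropouts as absent, that stopping sessions need not mean missing Post (payment is per completed assessment), that item 10 allows support instead of withdrawal, and that item 12 has retention reviewed quarterly. These make outcome-related loss uncertain, not impossible. The actions set out in item 12 are reviews, meetings and possible protocol changes, not an analysis rule.

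A reader might infer that the plan ignores missing data. It does not; the models and the dropout check are there. A reader might also infer a badly inflated error rate. If all leavers are selected on their unseen change with an assumed correlation of 0.5, a completers-only test rejects 14.2% of the time at 20% dropout and 23.3% at 35% (two-sided, nominal 5%). Nothing in the documents supports selection of that strength.

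**Conclusion.** The concern holds as a modest one. The efficacy test and its effect size rest on complete pairs, the stated principle is intent-to-treat, and the analysis that would reconcile the two is only exploratory.

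The true size is unknown. Under the assumed cases it is about 0.03–0.07 SD of change with 4–6% false improvement. It reaches about 0.10 SD and 8% only if correlation decays over visits and all leavers still gave Month 1 and Month 2 scores. It is zero if loss is unrelated to outcome, and can run either way. In every case shown it is below the sampling SD of about 0.24. Unlike sampling error, though, it is systematic and the confidence interval does not show it.

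It would be tempting to conclude that the pilot's efficacy result is invalid, or that withdrawal for deterioration must inflate it. Neither follows: efficacy is only initial, no go/no-go rule rests on the test, the power figures reproduce, and the documents do not say that withdrawn teens miss Post. When a teen is withdrawn is not questioned here.

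**What to change.** 1. **CRIES and EDE-Q.** Make the main test and effect size the Post-minus-Baseline contrast from a linear mixed model for repeated measures: REML, categorical time, all enrolled teens, all four visits, unstructured covariance, Kenward-Roger degrees of freedom. With 30 teens it may fail to converge (not tested here), so name a fallback in advance, for example multiple imputation of Post from Baseline and interim scores, and not a random intercept alone. Keep the paired t-test as a labelled observed-cases analysis.
2. **SF12.** Label the paired test observed-cases and report how many teens lack Post. No interim SF12 exists, so interim visits cannot correct it.
3. **Post assessment.** State whether teens who stop or are withdrawn are still invited to complete the already scheduled Post surveys, subject to consent and assent.

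**Cost.** A short rewording of item 13 and one protocol clarification. No new visits are needed: the surveys already run online (Section IV, item 2) and payment per assessment is already planned (Section VI, item 2). The estimate may be less favourable: at a true d of 0.64 with one or two deterioration leavers, the paired mean would be about 0.67–0.71 SD (0.64 + 0.03 to 0.64 + 0.07), against about 0.64 from the model. The gain in standard error is small (about 0–6%), and bias is only partly reduced if leaving depends on the unseen Post score.
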